### 11.2.2 Seriousness

A “serious” adverse event is defined in regulatory terminology as any untoward medical occurrence that:

1. Results in death.  
If death results from (progression of) the disease, the disease should be reported as event (SAE) itself.
2. Is life-threatening.  
(the patient was at risk of death at the time of the event; it does not refer to an event that hypothetically might have caused death if it were more severe).
3. Requires in-patient hospitalization or prolongation of existing hospitalization for  $\geq 24$  hours.
4. Results in persistent or significant disability or incapacity.
5. Is a congenital anomaly/birth defect
6. Is an important medical event  
Any event that does not meet the above criteria, but that in the judgment of the investigator jeopardizes the patient, may be considered for reporting as a serious adverse event. The event may require medical or surgical intervention to prevent one of the outcomes listed in the definition of “Serious Adverse Event”.  
For example: allergic bronchospasm requiring intensive treatment in an emergency room or at home; convulsions that may not result in hospitalization; development of drug abuse or drug dependency.

### 11.2.3 Relationship

Attribution categories for adverse events in relationship to protocol therapy are as follows:

Related – The AE is *clearly related* to the study treatment

Unrelated – The AE is *clearly NOT related* to the study treatment.

### 11.2.4 Prior experience

Expected events are those that have been previously identified as resulting from administration of the agent. An adverse event is considered unexpected, for expedited reporting purposes only, when either the type of event or the severity of the event is not listed in the current known adverse events listed in the agent clinical experience section of this protocol or Product Label.

### **11.3 Reporting Requirements for Adverse Events**

Adverse events, serious adverse events, deviations, violations, and unanticipated problems must be entered into the clinical trial management system (CTMS), OnCore, and must also be reported to the following entities according to the timelines mentioned in the chart below. Serious adverse events collection will start at the time patient signs consent until 28 days after the end of treatment. Adverse events will be collected from the time the research patient begins treatment until 28 days after the end of treatment. All adverse events/serious adverse events should be followed until resolution or stabilization.

Event Type	Coordinating Center/Medical Monitor	UCI IRB	Local IRB	Jazz Pharmaceuticals	Pfizer	CFCCC DSMB
Unanticipated Problem	Within 24 hours from date the site is aware of the event, the site should enter this information into OnCore. An email notification should also be sent via email to [contact] and [contact] .	Within 5 business days submit an Unanticipated Problem Report (UP) through Kuali Research Protocols . Current policy can be found here .	According to local institutional policies and guidelines	Within 1 business day of learning of the event. Submit all UPs to [contact] and submit any copies of the FDA submissions to [contact] when the FDA submission is made. All follow up information must be sent to Jazz Pharmaceuticals within 1 business day of PI's receipt of new information.	Within 1 business day of learning of the event. Submit all UPs via CIOMS form or a Pfizer approved SAE form.	Within 5 days from date PI is aware of the event. This information must be reported into OnCore.
AEs and SAEs (non-Unanticipated Problem)	Please refer to section 11.4 for reporting timeframes on AEs and SAEs	N/A		All SAEs should be reported in the same manner as a UP. All other adverse events will be reported to Jazz Pharmaceuticals in summary or line-item form upon Jazz Pharmaceuticals' request and at the conclusion of the study.	All SAEs should be reported in the same manner as a UP.	Please refer to section 11.4 for clarification on reporting timeframes for AEs and SAEs
Non-compliance	N/A	N/A		N/A	N/A	Please refer to section 11.4 for reportable deviations/violations
Serious or continuing non-compliance	Within 24 hours via email to [contact] and [contact] .	Within 5 business days submit a reportable event through Kuali Research Protocols .		N/A	N/A	Within 5 days from date PI is aware of the event.
Prospective/Planned Deviations	At least 5 business days prior to the event via email to [contact]	At least 48 hours prior to date the request is		N/A	N/A	At the time of progress review as aggregate reports

	and [contact] for approval.	needed by. Submit a Prospective Deviation Request form through Kuali Research Protocols .				
--	--	---	--	--	--	--

**11.4 Additional Reporting of Events from Investigators at Participating Sites to the Sponsor Investigator**

- Investigators at participating institutions must report AE, SAE, deviations, violations, and unanticipated problems according to their institutional policies.
- Investigators at participating institutions must also report AE, SAE, deviations, violations, and unanticipated problems to the PI of the coordinating center (or other entity such as a contract research organization) in the following timeframes:

**Adverse Event/ Serious Adverse Events**

Event Type	Reporting Timeframe to CFCCC DSMB (Notification is done by entering this information into OnCore within the timelines below)	Reporting Timeframe to Coordinating Center (Notification is done via email to [contact] and [contact] within the timelines below)
Serious Adverse Events (all attributions) that meet all of the following criteria: 
 
• Unexpected
 
• Grades 3-5
 
• Occurring during treatment or within 28 days of the end of treatment*
 
	5 business days from date the PI is aware of the event	24 hours from date the site is aware of the event.
Adverse Events that meet all of the following criteria: 
 
• Unexpected
 
• Study related (possibly, probably, or definitely)
 
• Grades 3-4
 
• Occurring during treatment or within 28 days of the end of treatment*
 
	5 business days from date the PI is aware of the event	24 hours from date the site is aware of the event.
All other Adverse Events and Serious Adverse Events should be reported as noted in the 'Reporting Requirements for Adverse Events' section	Prior to each scheduled progress review.	5 business days from the date the site is aware of the event
* Investigators are not obligated to actively seek information regarding the occurrence of new AEs or SAEs beginning after the 28-day post-treatment period. However, if the investigator learns of such an event and that event is deemed relevant to the study, he/she should promptly document and report the event.		

**Deviations/Violations**

Event Type	Reporting Timeframe to CFCCC DSMB (Notification is done by entering this information into OnCore within the timelines below)	Reporting Timeframe to Coordinating Center (Or other entity monitoring/coordinating the trial)
Violations as defined above (e.g. wrong dosage of drug administered, safety procedures not being conducted at specific time points).	5 business days from the date the PI is aware of the event	24 hours from the date the site is aware of the event
Deviations as defined above, including: 
 
• Planned deviations (e.g. rescheduling a visit that will be out of window due to a holiday)
 
• Unplanned deviations (e.g. rescheduled visit, a missed routine safety laboratory test for a participant with previously normal values)
 
	Prior to each scheduled progress review	5 business days from the date the site is aware of the event

## 12.0 AGENT INFORMATION

---

### 12.1 Glasdegib

Please refer to product label for more comprehensive information.

**Other names for the drug:** Daurismo

**Mechanism of action (or Product description):** Hedgehog pathway inhibitor

**Availability:** Provided by funder,

**How supplied:** Glasdegib will be supplied in 30 count pill bottles. Initial dose will be supplied in 100 mg tablets. If dose modifications are needed, Glasdegib will be supplied in 25 mg tablets.

**Storage and stability:** Store at 20°C to 25°C (68°F to 77°F); excursions permitted between 15°C to 30°C (59°F to 86°F).

**Route of administration for this study:** Oral dose, given daily in the morning with or without food

**Side effects:** Anemia, fatigue, hemorrhage, febrile neutropenia, musculoskeletal pain, nausea, edema, thrombocytopenia, dyspnea, decreased appetite, dysgeusia, mucositis, constipation, rash.

#### 12.1.1 Return and Retention of Study Drug

Remaining drug is to be destroyed, according to Chao Cancer Center Investigational Drug Services destruction policy. Participating sites are to follow their institutional practice for destruction of study drug.

#### 12.1.2 Drug Accountability/Subject Compliance

Records of study medications used, dosages administered, and intervals between visits will be kept during the study. Patients will be asked to fill out a pill diary and bring with them for review after each cycle of study treatment. (Appendix E)

Drug accountability will be noted at the completion of the trial. Patients will be asked to return all unused medication at the end of the study.

### 12.2 CPX-351

Please refer to product label for more comprehensive information.

**Other names for the drug:** Vyxeos; Liposomal Cytarabine and Daunorubicin

**Mechanism of action (or Product description):** liposomal formulation of cytarabine and daunorubicin in fixed 5:1 molar ratio which was developed to treat AML.

**Availability:** Provided by funder,

**How supplied:** CPX-351 will be supplied as 100mg cytarabine plus 44mg daunorubicin in a 50ml vial.

**Storage and stability:** Store unreconstituted VYXEOS vials in a refrigerator at 2°C to 8°C (36°F to 46°F) in an upright position. The vial should be stored in its original carton to protect from light.

**Route of administration for this study:** The appropriate number of vials of CPX-351 should be removed from the refrigerator prior to reconstitution. Reconstitute with 19 mL of sterile water for injection using a 20 mL syringe. Do not heat CPX-351. After reconstitution, invert vials gently 3-4 times and let rest for 15 minutes and repeat vial inversion prior to withdrawing drug from dilution. The concentration of the reconstituted dispersion is 5u/mL. CPX-351 should be diluted in approximately 500 mL of sodium chloride injection or dextrose injection.

The IV bags and infusion sets must follow the Vyxeos package insert). Per Vyxeos package insert, nondi(2-ethylhexyl)phthalate (DEHP) IV bags and infusion sets are not required. Aseptic technique must be strictly observed throughout the handling of CPX-351 since no bacteriostatic agent or preservative is present. The infusion of CPX-351 must be started within 4 hours of dilution. Vials are for single use only. Unused material should be recorded as such and discarded according to institutional policies. Procedures for proper handling and disposal of anticancer drugs should be implemented.

The infusion of CPX-351 will be performed through a central venous catheter, using an infusion pump to ensure that the drug is infused over the specific time period. Do not use an in-line filter. CPX-351 should never be given by intramuscular or subcutaneous route. Administer CPX-351 over approximately 90 minutes via an infusion pump. Flush the line to ensure the administration of the full dose.

**Side effects:** Hemorrhagic events, febrile neutropenia, rash, edema, nausea, mucositis, diarrhea, constipation, musculoskeletal pain, fatigue, abdominal pain, dyspnea, headache, cough, decreased appetite, arrhythmia, pneumonia, bacteremia, chills, sleep disorders, and vomiting

## **13.0 STATISTICAL CONSIDERATIONS**

---

### **13.1 Study Design**

This is an investigator-initiated trial which will evaluate the outcome of the combination of CPX-351 and Glasdegib in patients with newly diagnosed AML. This is a single-arm, open-label, Phase-IIA clinical trial to estimate the efficacy and tolerability of the combination of CPX-351 and Glasdegib in the study population.

UC Irvine will be the primary site of enrollment and additional sites within the University of California Hematologic Malignancies Consortium (UCHMC), including UCSF, UCLA, UCSD, and UCD can be added. Total of 1-5 U.S. centers. Enrollment can occur at any site as long as the trial is open at that site.

### **13.2 Data Analyses Plans**

#### **13.2.1 Primary Objectives**

For efficacy, the primary objective is to estimate proportion of evaluable participants who are event-free at six months (EFS6) and compare to the historical figure of 50 percent.

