	
 
9. History of GI malabsorptive disease
 
10. Has a known additional malignancy that is progressing or requires active treatment. Exceptions include basal cell carcinoma of the skin, squamous cell carcinoma of the skin, or in situ cervical cancer that has undergone potentially curative therapy
 
11. Known HIV infection
 
12. Active hepatitis B or hepatitis C infection (patients who successfully completed curative hepatitis C therapy can be enrolled)
 
13. Any uncontrolled infection, active bacterial or viral infection manifesting as fevers or hemodynamic instability within the past 72 hours
 
14. Proven active invasive fungal infection
 
15. Is pregnant or breastfeeding, or expecting to conceive or father children within the projected duration of the trial, starting with the pre-screening or screening visit through 120 days after the last dose of trial treatment
 
16. Severe or uncontrolled medical disorder that would, in the investigator’s opinion, impair ability to receive study treatment (i.e., uncontrolled diabetes, chronic renal disease, chronic pulmonary disease or active, uncontrolled infection, psychiatric illness/social situations that would limit compliance with study requirements
 
17. Current or anticipated use of other investigational agents
 
18. For patients with prior anthracycline exposure, the cumulative life-time dose should not exceed 386mg/m^2 at the time of study entry (to convert different anthracycline to daunorubicin-equivalent, see Appendix H for conversion factors)
 

Study Product(s)	CPX-351 and Glasdegib
Duration of administration	
 
• CPX-351 will be administer during Induction on days 1, 3 and 5. Glasdegib will be given starting on day 6 and continuing until beginning of consolidation
 
• Consolidation can be either 1 or 2 cycles. CPX-351 will be administered during days 1 and 3. Glasdegib will begin on day 4 and continue daily
 
• If the patient is a candidate for HSCT and moves forward with HSCT, then Glasdegib will be discontinued at least 7 days prior
 

	
 
• During Maintenance, Glasdegib will be taken daily for up to 1 year
 

Reference therapy	Lancet Phase II CPX-351 versus 7+3. Blood 2014

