Based on the results of the phase I trial of the combination of Glasdegib with standard chemotherapy, a phase II open-label study of Glasdegib in combination with cytarabine and daunorubicin with patients with newly diagnosed AML or high-risk MDS was initiated [25]. Patients received Glasdegib started on day -3 at 100mg orally daily in continuous 28 days cycles. They also received cytarabine at 100mg/m^2 on day 1-7 and daunorubicin at 60mg/m^2 on day 1-3. Once in remission, they received cytarabine consolidation at 1gm/m^2 twice daily on days 1, 3, 5 of each cycle for 2-4 cycles total. This was followed by maintenance Glasdegib for up to 6 cycles. The complete remission rate was 46%. Among patients older than 55, the complete remission rate was 40%. Among all 69 patients, the median overall survival was 14.9 months. The most common treatment related adverse reactions were diarrhea and nausea. The combination was well tolerated.

In the non-intensive arm of the phase II trial with LDAC with Glasdegib, there were several genes that correlated with improved OS [26]. Lower levels of expression of FOXM1 and MSI2 and higher expression levels of BCL2 and CCND2 correlated with improved overall survival. In the intensive treatment arm with Glasdegib and cytarabine/daunorubicin, higher PTCH1 expression correlated with improved overall survival. Furthermore, in the intensive arm, mutations in FLT3, TP53, CEP170, NPM1 and ANKRD26 correlated with overall survival. Interesting to note, that patients with AML with mutated FLT3 (which is generally a poor risk group) did better than AML with wild type FLT3. Therefore, we will be measuring some of these genes to see if this observation of their correlation with improved overall survival is confirmed.

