### **1.5.3 Further development of CPX-351**

In the phase II trial, the outcomes were compared of CPX-351 versus traditional cytarabine/daunorubicin (7+3) chemotherapy in 126 patients with newly diagnosed AML [32]. CPX-351 had higher response rates than traditional cytarabine/daunorubicin (7+3) chemotherapy at 66.7% versus 51.2% with p=0.07 which met the predefined criteria of p<0.1. There was a prolongation of event-free survival as well as overall survival but this was not significant. The recovery after cytopenias were more prolonged after CPX-351 with more grade 3-4 infections but without increased deaths due to infection. Aside for risk of infection, patients did have diarrhea, nausea, edema, constipation, rash, febrile neutropenia. However, these side effects were also seen with the cytarabine/daunorubicin arm. Furthermore, the 60-day mortality was not increased in the CPX-351 arm. This provided the rationale for a phase III trial.

In the phase 3 clinical trial, CPX-351 has improved overall survival rates, event-free survival and response rate (complete response and complete responses with incomplete recovery) to traditional 7+3 chemotherapy in the patients with previously untreated AML with MDS related changes as well as AML evolving out of MDS [33]. There was a prolongation in recovery of cytopenias seen again. There were similar rates of grade 3-5 infections between CPX-351 and standard cytarabine/daunorubicin induction chemotherapy. At median follow-up of 21 months, the median overall survival was 9.5 months in CPX-351 arm versus 5.9 months in the standard 7+3 arm. The complete remission/complete remission with incomplete recovery (CR/CRi) rate were 47% with CPX-351 versus 33% in 7+3 arm (p=0.008). The duration of remission was similar between the two groups at 6.9 months versus 6.1 months in CPX-351 and 7+3 arm, respectively. As a result of improved response rates, more patients receiving CPX-351 were also able to go to transplant than 7+3 arm at 34% versus 25% p=0.049 [34]. Furthermore, as an exploratory endpoint, there was improved post-transplant survival in patients who received CPX-351 versus 7+3 chemotherapy [35].

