## **10.4 Event-free survival**

Event-free survival is defined as the time from screening biopsy to the date of confirmed disease progression, relapse from CR/CRi, treatment failure, or death, whichever comes first. This was chosen as an endpoint for several reasons. It is known to incorporate several endpoints of interest including efficacy of the treatment as well as toxicity that both contribute to the outcome of the patient. Complete remission may not capture the full benefits of Glasdegib since the drug may prevent relapse through different mechanisms than enhanced cytotoxicity.

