### 13.2.3 Primary Analysis

The null hypothesis is that EFS6 is 50%. The alternative hypothesis is that EFS6 will be 65% or more. The figure of 65% is the minimum thought to indicate the treatment regimen is worthy of further study. We will construct an exact (Clopper-Pearson), one-sided (lower), 90% confidence interval about the observed EFS6. If that the lower limit of that confidence interval is greater than 0.5, the treatment regimen will be deemed worthy of further study.

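### The 50% historical EFS6 has no stated source and sits above what the protocol's own CPX-351 data in this disease imply, so a real gain over CPX-351 alone could very probably be declared not worth pursuing

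*Combined protocol and SAP*

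**What the plan says.** Section 13.2.1 aims to "estimate proportion of evaluable participants who are event-free at six months (EFS6) and compare to the historical figure of 50 percent". Section 13.2.3 adds "The null hypothesis is that EFS6 is 50" per cent, sets 65% as the smallest rate of interest, and calls the regimen worthy of further study only if the exact one-sided 90% lower bound exceeds 0.5. Section 13.3 labels the 50% a historical-control value. None of these sections gives a citation, a population or an event definition for it, and the protocol quotes no 6-month EFS for any trial.

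Section 10.4 runs EFS from the screening biopsy to confirmed progression, "relapse from CR/CRi, treatment failure, or death, whichever comes first". Treatment failure is neither defined nor dated. Section 10.2 defines refractory disease as no CR at the end of induction; Appendix E defines resistant disease as no CR or CRi; the Study Schema footnote ends treatment for induction failure. None of the three is tied to EFS.

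On CPX-351, section 1.5.3 gives two trials:
- **Phase 3**, in AML with MDS-related changes or arising from MDS (the Study Summary rationale says secondary AML, ages 60-75): "The complete remission/complete remission with incomplete recovery (CR/CRi) rate were 47% with CPX-351 versus 33% in 7+3 arm", with remission lasting 6.9 months on CPX-351.
- **Phase II**, in newly diagnosed AML: "CPX-351 had higher response rates than traditional cytarabine/daunorubicin (7+3) chemotherapy at 66.7% versus 51.2" per cent. The Study Summary names this trial as reference therapy: "Phase II CPX-351 versus 7+3. Blood 2014".

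**The concern.** A patient who never reaches CR/CRi would ordinarily have an early EFS event, so the share event-free at six months should not exceed the share who respond, and should fall below it once relapses and deaths among responders are taken off. A benchmark of 50% is hard to square with a 47% response rate in the same disease.

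The whole conclusion turns on this number. If CPX-351 alone gives an EFS6 well below 50% in these patients, the trial can return a negative verdict on a combination that is materially better than its backbone, and the label *historical* would invite readers to conclude that glasdegib added nothing.

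**Working it through.** **1. The plan's own figures.** With n = 28, entering 28p as the count in the Clopper-Pearson formula gives lower bounds of 46.1%, 51.1% and 56.3% at p = 60%, 65% and 70%. These match the table in 13.3.

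The smallest passing counts are:
- n = 28: 18 (bound 0.504; 17 gives 0.468).
- n = 30: 20 (bound 0.534; 19 gives 0.49987, just short).

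The power at 65% is P(X ≥ 18 | 28, 0.65) = 61.6% and P(X ≥ 20 | 30, 0.65) = 50.8%. The 90% stated in 13.3 does not reproduce.

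**2. Does response cap EFS6?** Assume no CR/CRi by the end of induction or re-induction is an event. The latest date is 28 days (screening window) + 60 (induction, 5.2) + 60 (re-induction, 5.3) = 148 days after biopsy, which is inside six months. Under that reading EFS6 ≤ CR/CRi rate, so at most 47% on the phase 3 figure. For EFS6 to be 50%, 0.50/0.47 = 106% of responders would have to be event-free.

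**3. Allowing for relapse.** Further assumptions: 6.9 months is a median, loss of remission is exponential, and remission is reached 1 to 3.5 months after biopsy. A responder must then stay in remission for t = 5 to 2.5 months.

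EFS6 = 0.47 × exp(−ln 2 × t/6.9)
- t = 5: 0.47 × 0.605 = 28%
- t = 2.5: 0.47 × 0.778 = 37%

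**4. Uncertainty in the 47%.** The arm size is not given. Assuming about 150 of the 309 patients, the 95% interval is roughly 39-55%. At 55%, the same formula gives 0.55 × 0.605 = 33% to 0.55 × 0.778 = 43%.

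**5. The phase II trial.** EFS6 of 50% needs 0.50/0.667 = 75% of responders event-free at month 6. Borrowing the phase 3 remission duration gives 0.667 × 0.605 = 40% to 0.667 × 0.778 = 52%. So 50% is not excluded here.

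**6. Chance of a go under the stated rule.**

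| True EFS6 | n = 30 (needs 20) | n = 28 (needs 18) |
|---|---|---|
| 40% | 0.3% | 0.8% |
| 45% | 1.4% | 3.1% |
| 50% | 4.9% | 9.2% |
| 60% | 29% | 40% |
| 65% | 51% | 62% |

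**7. How much the benchmark matters (illustration only).** With the same 30 patients and the same exact bound:
- Null 35%: 15/30 needed, false-positive rate 6.5%, a true 50% passes with 57%.
- Null 30%: 13/30 needed, false-positive rate 8.4%, a true 50% passes with 82%.

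**The case against.** A reader might infer that 50% cannot be a CPX-351 figure and that a better regimen would certainly be rejected. The documents do not support that, for five reasons.

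- **The cap is conditional.** It needs treatment failure to mean no CR/CRi, which sections 2.1 and 10.4 do not say.
- **The protocol never claims that 50% is the CPX-351 rate in secondary AML.** Its named reference is the phase II trial, which is compatible with 50%. That the figure came from that trial, or from a different population, is inference; the source is not visible.
- **The 47% is a point estimate from ages 60-75, while this trial enrols from 18.** Younger patients may do better. If older patients have 31%, the under-60 share needed to make 50% right is (0.50 − 0.31)/(0.60 − 0.31) = 66% when younger patients have 60%, but 49% at 70% and 39% at 80%. None of these rates is in the documents.
- **Evaluable is undefined for efficacy.** Dropping 6% of patients, all non-responders, turns 47% into 0.47/0.94 = 50%.
- **The glasdegib plus 7+3 trial does not help.** "The complete remission rate was 46%. Among patients older than 55, the complete remission rate was 40" per cent is CR alone, in AML or high-risk MDS, so it cannot cap an endpoint that accepts CRi.

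The best defence is section 13.2.3 itself. It sets 65% as the minimum of interest, so a regimen at 45-50% is deliberately not advanced. A demanding hurdle in an uncontrolled trial is defensible.

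All of this stands, and it removes *cannot*. It does not supply a source for the 50% or explain its distance from the phase 3 data. A hurdle chosen by judgement is also not a historical control, which is how 13.2.1 and 13.3 present it.

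**Conclusion.** The benchmark is unsourced and conflicts with the only CPX-351 results the protocol quotes in this disease, provided that failure to reach CR/CRi is an EFS event. Under that reading the phase 3 data cap EFS6 at 47%; with exponential loss of remission from a 6.9-month median and remission 1 to 3.5 months after biopsy, they imply about 28-37%. They describe ages 60-75 and carry sampling error, so the right figure for this trial's population may be higher.

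If CPX-351 alone is near that range, a combination reaching 45-50% would miss the criterion at least nine times in ten. The documents support *could very probably be declared not worthy of further study*. They do not support certain rejection, nor any particular replacement value. The overstated power in 13.3 is a separate error, but it sits in the section that has to be re-derived.

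**What to change.** 1. In 10.4, state that no CR/CRi by the end of induction or re-induction is treatment failure for EFS, give its event date, and align this with 10.2 and Appendix E. Define evaluable so that non-responders and early deaths stay in the denominator.
2. In 13.2 and 13.3, cite a benchmark with the same event definition and disease, age-weighted if patients under 60 enrol. Restate the null, target and table with exact error rates, replacing the 90% power with the computed value (62% at n = 28 and 51% at n = 30 under the present 50% versus 65%).
3. If 50% is kept, call it a fixed go threshold. State that missing it does not show the combination is no better than CPX-351. Report EFS6 with its interval in patients aged 60-75 against the phase 3 figure, noting any difference in event definition.

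Cost: items 1 and 3 are wording plus one descriptive analysis, with no added visits. Item 2 needs a 6-month EFS figure from outside the protocol. The sample size should be fixed only after the new null and target are chosen; holding 50% versus 65% at 90% power would take about 70 (normal approximation) to 79 (exact) patients. The downside is that a lower benchmark looks less ambitious; if 50% stays, a negative result supports a narrower conclusion.
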